## Table 1 Schedule of Activities – Main Table (cont.)

1. If participants discontinue or withdraw from the study treatment prematurely, the participants should complete the Early Termination visit and attend the Follow-up visit normally done at the end of the study, 4 weeks after the last dose of study medication. If the discontinuation or withdrawal happens less than 14 days after a site visit, participants will have a reduced number of assessments.
2. If participants discontinue or withdraw from the study treatment prematurely, the participants should complete the Early Termination visit and attend the Follow-up visit normally done at the end of the study, 4 weeks after the last dose of study medication. If the discontinuation or withdrawal happens 14 days or more after a site visit, participants will have a full assessment.
3. The details of the specific order of assessments can be found in the Study Procedures Manual, which must be adhered to.
4. Visits exclusively for participants on warfarin to monitor potential need for dose adjustment of warfarin. The visits will happen 7 days after the first dose of RG7774/ placebo (at Day 7) and 7 days after the last dose of RG7774/ placebo (typically on Week 37, or earlier in case of discontinuing the study prematurely).
5. Telephone interview to assess for any clinically significant symptoms and/or new/ changed medication.
6. Screening urine pregnancy test for women of child-bearing potential (WOCBP) prior to first dose of RG7774 or placebo. Additional pregnancy tests can be performed anytime during the study at the discretion of the Investigator.
7. Full physical examination as per protocol.
- 7a. Height and weight will be recorded at the Day 1 visit only. Only weight will be measured at the Week 36 or Early Termination visits.
8. To be administered by masked site staff prior to any other visit assessments being performed on that day. If required, the questionnaires can be administered via telephone one business day prior to the visit. Confirmation that there are no changes should be obtained on the day of the site visit.
9. ECG (12-lead) will be obtained pre-dose on Day 1. All ECGs (12-lead) will be performed in triplicate, 1-2 minutes apart within 5 minutes.
10. Hormonal panel for postmenopausal women only.
11. HbA1c measurement is obtained from the same sample as hematology, except for Week 48.
12. Blood chemistry at Day 1 will only be analyzed for C-reactive protein (CRP).

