### **7.1 DISCONTINUATION OF STUDY TREATMENT**

See the SoA (Section [1.3](#)) for data to be collected at the time of treatment discontinuation and follow-up and for any further evaluations that need to be completed.

Reasons for discontinuation of study treatment may include, but are not limited to, the following:

- Participant withdrawal of consent at any time
- Participant non-compliant to study treatment
- Pregnancy
- Investigator or Sponsor determination that treatment discontinuation is in the best interest of the participant.

Every effort should be made to obtain information regarding the reason why participants withdraw from study treatment, including cases of non-compliance with treatment administration. The primary reason for premature study treatment discontinuation should be documented on the appropriate eCRF.

Participants who terminate study treatment prematurely for any reason will be asked to return to the clinic for a study completion/early termination visit (see Section [8.10.3](#)) and may undergo follow-up assessments (see Section [8.10.4](#)), unless the participant withdrew consent. Two different sets of assessments will be available to the participants depending on the date of discontinuation relative to the last site visit (see Section [1.3](#)).

- If the discontinuation happens within 14 days after a site visit, fewer assessments will be performed. This will avoid the unnecessary repetition of assessments whose outcomes generally do not vary in such time window.
- If the early termination visit happens more than 14 days after a site visit a complete set of assessments needs to be performed.

Please refer to Section [8.10.2](#) for those participants taking warfarin.

For participants who require rescue medication due to disease-related events (see Section [6.5.3](#) and Section [8.3.7](#)) that are considered natural disease progression by the

Investigator, the study treatment should not be discontinued. However, if the disease-related events are not considered natural progression of the disease and thus qualify as AEs, study treatment may be discontinued upon Investigator discretion or Sponsor decision. The occurrence and type of events leading to rescue medication must be recorded.

Please refer to SoA for further details (Section 1.3) for data to be collected at the time of study discontinuation and at safety and follow-up visits, and for any further evaluations that need to be completed.

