## **7.2 PARTICIPANT DISCONTINUATION/WITHDRAWAL FROM THE STUDY**

Participants have the right to voluntarily withdraw from the study at any time for any reason.

In addition, the Investigator has the right to withdraw a participant from the study for medical conditions that the Investigator or Sponsor determines, may jeopardize the participant's safety if he/she continues in the study.

If possible, information on reason for withdrawal from the study should be obtained. The primary reason for withdrawal from the study should be documented on the appropriate eCRF. Participants will not be followed for any reason after consent has been withdrawn.

When a participant voluntarily withdraws from the study, or is withdrawn by the Investigator, samples collected until the date of withdrawal will be analyzed, unless the participant specifically requests for these to be discarded or local laws require their immediate destruction. However, if samples have been tested prior to withdrawal, results from those tests will be used as part of the overall research data. A participant's withdrawal from this study does not, by itself, constitute withdrawal of samples donated to the Research Biosample Repository (RBR).

Participants who withdraw from the study for safety or for other reasons will not be replaced.

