### **8.10.3 Assessments at Study Treatment Completion / Early Termination Visit**

Participants who complete the 36-week treatment phase will be asked to return to the clinic for two visits with fewer assessments compared to the regular visits:

- A safety follow-up visit, 28 ( $\pm 7$ ) days after the final dose of study treatment (week 40 visit),
- An efficacy visit, 84 ( $\pm 7$ ) days after the final dose of study treatment (week 48 visit).

Participants who discontinue from the study treatment phase early, will have an early termination visit and be asked to return to the clinic 28 ( $\pm 7$ ) days after the final dose of study treatment for a safety follow-up visit.

- if the early termination visit occurs within 14 days of the last site visit, the list of assessments to be performed will be reduced.
- If the early termination visit happens more than 14 days after a site visit a complete set of assessments needs to be performed.

See Section [1.3](#) ([Table 2](#)), and Sections [8.1](#) and [8.2](#) for further details.

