### **9.2 SAMPLE SIZE DETERMINATION**

A total of 135 participants are expected to be randomized 1:1:1 to the three groups (45 participants per group). Based on Fisher's exact test, assuming the proportion of participants with  $\geq 2$  step improvement in the ETDRS DRSS to be 15% for placebo and 40% to 45% under active treatment, 40 participants completing the study per group provide between 74% and 88% power based on a 2-sided significance level of 0.1. Allowing for about 10% of the participants randomized to not complete the study and hence not have an assessment of the primary endpoint at week 36, a total of 135 participants (45 participants per group) was selected to obtain 120 completers. If the rate of participants not completing the study is larger than 10%, the sample size may be increased beyond 135 participants with the aim of achieving approximately 45 completers per group.

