### 9.4.2 Efficacy Analyses

For the primary and exploratory efficacy analyses, see [Table 7](#).

All efficacy data will be summarized by randomized treatment group and visit for the ITT population.

Participants in whom any of the events (i) to (iii) described in Section 6.5.3 occur in either eye, or participants who require rescue treatment prior to the week 36 assessment will still be considered as completing participants and will enter the analysis as non-responders at the visit at which the event occurs as well as all subsequent visits.

The primary endpoint will be analyzed using GEE with a binomial distribution using a logit link function for odds ratios and unstructured covariance. In case of convergence issues, an alternative covariance structure will be used. The model will include categorical covariates for treatment group, visit, and visit by treatment group interaction term. Also the baseline stratification factors will be added. Least squares means on the probability scale for each treatment group with the corresponding 90% confidence intervals and odds ratios relative to the placebo group will be computed for each visit. Full details of the statistical analysis will be described in a separate document prior to any unmasking of the study.

In accordance with the ITT principle, assessments at all visits will be included in the analysis. This includes any assessments made at visits while the participant is on randomized study treatment as well as any assessments made at visits after randomized study treatment has been terminated.

If visits occur as described in Section 1.3, a response assessment at week 36 will be available for all participants. Despite best efforts, there may be missing response assessments at week 36 (e.g., for participants withdrawing consent or being lost to follow-up). *The statistical methodology to deal with missing data will be described in a separate technical document prior to any unmasking of the study.*

The proposed methodology is known to render unbiased effect estimates only under the restrictive missing completely at random assumption (Liang and Zeger, 1986). Therefore, if the amount of total missing data (across patients and visits) exceeds 10% of all expected data, sensitivity *analyses* will be carried out (Molenbergs and Verbeke, 2005).

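### The efficacy section says the scheduled visits give everyone a Week 36 response, but no Week 36 assessment is scheduled for participants who stop study drug early

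*Combined protocol and SAP*

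**What the plan says.** Section 9.4.2 sets out an intention-to-treat analysis. It includes "any assessments made at visits after randomized study treatment has been terminated" and then asserts: "If visits occur as described in Section 1.3, a response assessment at week 36 will be available for all participants". Its examples of how a Week 36 grade might still be missing are consent withdrawal and loss to follow-up; stopping study drug is not among them.

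The visit instructions for early stoppers are in three places:

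- **Section 1.3, Table 1 footnotes 1 and 2:** the instruction for participants who stop study treatment is to "complete the Early Termination visit and attend the Follow-up visit normally done at the end of the study, 4 weeks after the last dose".
- **Section 7.1:** "Participants who terminate study treatment prematurely for any reason will be asked to return to the clinic for a study completion/early termination visit". Follow-up assessments after that visit are optional in wording.
- **Section 8.10.3:** "Participants who discontinue from the study treatment phase early, will have an early termination visit and be asked to return to the clinic". That return visit is timed at four weeks (±7 days) from the last dose. The Week 40 and Week 48 visits are described for those who complete the 36-week treatment phase.

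Three other statements bear on the point. Under Section 9.4.2, participants with a Section 6.5.3 event or rescue "will enter the analysis as non-responders at the visit at which the event occurs as well as all subsequent visits". Section 7.2 rules out follow-up once consent is withdrawn: "Participants will not be followed for any reason after consent has been withdrawn". Section 9.2 allows for about 10% of participants to "not complete the study and hence not have an assessment of the primary endpoint at week 36".

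**The concern.** The analysis section intends a Week 36 response whether or not the participant stayed on drug, and it relies on Section 1.3 to supply it. Section 1.3 does not. Even with perfect adherence to the schedule, an event-free participant who stops at, say, Week 16 has no Week 36 photograph.

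Section 9.4.2 acknowledges that its GEE is unbiased only if data are missing completely at random. Here the missing grade follows directly from stopping drug, so the assumption is open to doubt. The only stated safeguard is that sensitivity analyses are run if total missing data, over all patients and visits, exceed 10%. Missingness concentrated at Week 36, the only visit that defines the primary endpoint, is diluted by the earlier visits. A separate missing-data document can choose a method, but it cannot recover photographs that were never taken.

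**Working it through.** **1. The plan's own figures.** Inputs from Section 9.2: 15% response on placebo, 40% to 45% on active, two-sided alpha 0.10, 40 completers per group. Exact enumeration of Fisher's test gives 75.5% and 87.5% power, against 74% and 88% stated. For enrolment, 40 / (1 − 0.10) = 44.4, rounded up to 45 per group and 135 in total. The sample-size arithmetic is sound; the problem lies in the schedule.

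**2. Who is affected.**

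- Event or rescue before Week 36: non-responder by rule, so not affected.
- Consent withdrawn or lost to follow-up: missing, and not recoverable.
- Event-free, stopped drug, still consenting: Early Termination visit and 28-day visit only.

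In the third group a Week 36 grade can arise by chance. With last dose at week t, the 28-day visit falls between t + 3 and t + 5 weeks, and the Week 36 window is Weeks 35 to 37. Overlap needs t + 5 ≥ 35 and t + 3 ≤ 37, so t must lie between 30 and 34. An Early Termination visit may also fall inside the window. Anyone stopping before about Week 30 has no such route.

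**3. How many.** The plan does not say. Its 10% allowance gives 0.10 × 135 = 13.5, so 13 to 14 participants. This is an upper bound under the plan's own allowance, because it also contains withdrawals and losses.

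**4. Effect on the comparison.** This is an illustration with Fisher's exact test (two-sided), one active arm against placebo, and observed counts at the planned 15% and 40%.

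| Missing per arm | Observed, placebo vs active | Handling of missing | Counts compared | p |
|---|---|---|---|---|
| 5 of 45 | 6/40 vs 16/40 | observed only | 6/40 vs 16/40 | 0.023 |
| 5 of 45 | 6/40 vs 16/40 | all non-responders | 6/45 vs 16/45 | 0.026 |
| 5 of 45 | 6/40 vs 16/40 | best case for drug | 6/45 vs 21/45 | 0.001 |
| 5 of 45 | 6/40 vs 16/40 | worst case for drug | 11/45 vs 16/45 | 0.358 |
| 3 of 45 | 6/42 vs 17/42 | worst case for drug | 9/45 vs 17/45 | 0.103 |
| 2 of 45 | 6/43 vs 17/43 | worst case for drug | 8/45 vs 17/45 | 0.059 |

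**5. The 10% trigger.** Assume the expected data are the four post-baseline site visits up to Week 36 (Weeks 4, 12, 24 and 36): 135 × 4 = 540 grades, and 10% is 54.

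- 13 to 14 participants stop after Week 24, one grade lost each: 13/540 = 2.4% to 14/540 = 2.6%.
- All of them stop before Week 4, four grades lost each: 52/540 = 9.6% to 56/540 = 10.4%.
- If earlier visits are complete, 54 of the 135 Week 36 grades (54/135 = 40%) could be missing without exceeding the trigger.

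**The case against.** The strongest reply is that the gap is narrow and the consequence modest. The route most clearly related to outcome is closed, since events and rescue count as non-response and Section 7.1 keeps those with natural progression on drug. The remaining stoppers may have stopped for reasons unrelated to retinopathy grade. No passage says they must leave the study or skip Week 36. Section 4.1.2 calls the 28-day period one of safety and efficacy follow-up, so they may supply a late photograph. Section 9.2 already allows for 10% without a Week 36 grade. Counting all the missing as non-responders moves p only from 0.023 to 0.026, the 0.358 bound is extreme, Fisher is not the analysis model, and this is an exploratory Phase II trial whose missing-data methods are set out elsewhere.

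Much of this stands as a limit on size. The affected group is event-free stoppers only, and no bias has been demonstrated. The p-value range is a set of bounds, and the 40% figure describes the trigger rather than a likely outcome. In the text available for this review, Table 1 is too broken to confirm whether the 28-day visit includes photography.

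It does not remove the contradiction. The footnotes to Table 1 give early stoppers their own path, and sites will follow that explicit instruction. A photograph 28 days after an early last dose is not a Week 36 grade. The 9.2 allowance protects power, not against bias from who is missing.

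**Conclusion.** The concern holds. The Section 9.4.2 statement about Week 36 availability is false as written for participants who stop study drug early without an event, because Sections 1.3, 7.1 and 8.10.3 schedule nothing for them at Week 36 other than by coincidence of timing. The GEE still runs and uses their earlier grades, but their Week 36 contribution rests on an assumption the plan itself regards as restrictive.

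The size is uncertain: at most about 13 to 14 participants under the plan's allowance, and probably fewer. At the planned 15% and 40% rates, two unobserved per arm could not overturn a result at the 0.10 level even in the worst case; three could, marginally. The 10% trigger would probably not be met, on the assumption that the four post-baseline site visits are the denominator. This should be fixed, although it does not invalidate the analysis. Confidence is high on the inconsistency; the amount of bias cannot be determined from the documents.

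**What to change.** - Reconcile Section 1.3 (Table 1 footnotes 1 and 2), Section 7.1 and Section 8.10.3 with Section 9.4.2. Participants who stop study drug but do not withdraw consent should be asked to attend the existing Week 36 visit for outcome collection only: study-eye seven-field photography, BCVA and SD-OCT.
- Correct the Section 9.4.2 sentence so that it claims only what the schedule delivers.
- In the separate missing-data document, unless it is already there, pre-specify a sensitivity analysis that counts discontinuers without a Week 36 grade as non-responders. Run it whether or not the 10% trigger is met.

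The cost is one already-defined visit for at most about 13 to 14 participants, one extra table and some protocol wording. The drawback is the visit burden on people who are no longer taking study drug. Dosing, rescue and stopping rules are unchanged, and the Section 7.2 rule on withdrawn consent is respected.

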**Table 7 Efficacy Statistical Analysis Methods**

Endpoints	Statistical Analysis Methods

Primary
 
Proportion of participants with <math>\geq 2</math> step improvement in ETDRS DRSS from baseline at Week 36 measured in the study eye.
	
Generalized Estimating Equations (GEE) with a binomial distribution taking into account repeated measures within each participant.

Secondary
 
Incidence of ASNV, new PDR, new DME, and pre-existing DME requiring intervention.
 
Change from baseline in BCVA at Week 36 in the study eye.
	
Descriptive summaries of the number, frequency and percentage of participants experiencing the types of events.
 
Analysis of variance model for longitudinal data taking into account repeated measures within each participant

Exploratory
 
Proportion of participants with <math>\geq 2</math> step worsening in ETDRS DRSS from baseline at Week 36 measured in the study eye.
	
GEE with a binomial distribution taking into account repeated measures within each participant.

Proportion of participants with <math>\geq 3</math> step improvement in ETDRS DRSS from baseline measured in both eyes at post-baseline visits.
	
Analysis performed in subgroup of ITT population with bilateral disease. Modeling will be similar as for the primary endpoint.

Proportion of participants with <math>\geq 3</math> step worsening in ETDRS DRSS from baseline measured in both eyes at post-baseline visits.
	
Analysis performed in subgroup of ITT population with bilateral disease. Modeling will be similar as for the primary endpoint.

Proportion of participants with either a stable (<math>\pm 1</math> step change), worsened (<math>>1</math> step increase) or improved (<math><1</math> step decrease) DRSS between week 36 and week 48.
	
Modeling will be similar as for the primary endpoint.

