## **2. INTRODUCTION**

### **2.1 STUDY RATIONALE**

The endocannabinoid system has been involved in the pathology of diabetes mellitus (DM) and its complications, including diabetic retinopathy (DR) ([Behl et al. 2016](#), [Gruden et al. 2016](#)). RG7774 (also referred to as RO6868847) is a synthetic small molecule that is a potent cannabinoid 2 (CB2) receptor agonist, with high selectivity for CB2 versus CB1 receptors, as shown by pharmacological data and by the lack of psychotropic effects of central CB1 receptor activation at the doses tested to date in humans. RG7774 is being developed for patients suffering from DR.

The primary objective of the current study BP41321 is to assess the safety, tolerability and the effect of oral administration of RG7774 on the severity of DR in patients with moderately severe to severe non-proliferative diabetic retinopathy (NPDR) and good vision.

The secondary objectives are to further evaluate the potential of RG7774 to prevent progression of DR, as determined by the incidence of sight-threatening events (e.g., diabetic macular edema [DME] or proliferative diabetic retinopathy [PDR]), and to assess the effect of RG7774 on best-corrected visual acuity (BCVA).

Results from nonclinical pharmacology, pharmacokinetic (PK), and toxicology studies and the outcomes of the healthy volunteer entry-in-human single-ascending dose (SAD), multiple-ascending-dose (MAD), food-effect (FE) study (EIH, BP40387), as well as the itraconazole drug-drug interaction (DDI) study (BP41274) have been considered in the development of protocol BP41321.

The study results from the current study BP41321 will be used to support further clinical development of RG7774.

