**Table 3 Objectives and Endpoints**

Objectives	Endpoints
Primary	

 
• Assess the effect of RG7774 on the severity of DR.
 
• Evaluate the safety and tolerability of RG7774.
 
	
 
• Proportion of participants with <math>\geq 2</math> step improvement in the Early Treatment Diabetic Retinopathy Study (ETDRS) DR severity score (DRSS) from baseline at Week 36 measured in the study eye.
 
• Frequency and severity of adverse events.
 

Secondary	

 
• Assess the effect of RG7774 on progression to vision-threatening DR.
 
• Assess the effect of RG7774 on visual acuity.
 
	
 
• Incidence of anterior segment neovascularization (ASNV), new PDR, new DME, and pre-existing DME requiring intervention.
 
• Change from baseline in BCVA at Week 36 in the study eye.
 

Exploratory	

 
• Assess the effect of RG7774 on DR worsening.
 
	
 
• Proportion of participants with <math>\geq 2</math> step worsening in ETDRS DRSS from baseline at Week 36 measured in the study eye
 

 
• Assess the effect of RG7774 on DR severity at a participant level.
 
	
 
• Proportion of participants with <math>\geq 3</math> step improvement in ETDRS DRSS from baseline at post-baseline visits measured in both eyes
 
• Proportion of participants with <math>\geq 3</math> step worsening from baseline at post-baseline visits measured in both eyes.
 

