#### **4.2.4 Rationale for Response Definition and Study Eye Selection**

The primary endpoint will be the proportion of participants with a  $\geq 2$ -step improvement from baseline in ETDRS DRSS at 36 weeks, measured in the study eye. At any time, new ASNV, new PDR, new DME and pre-existing DME requiring intervention (see permitted therapies Section [6.5.1](#)), occurring in the study eye will classify a participant as a non-responder for the primary analysis, as all these events imply progression of the disease.

Since RG7774 is an oral treatment with expected bilateral effects, the Sponsor will evaluate an in-patient (sum of both eyes) DRSS improvement of  $\geq 3$  steps in participants with two eligible eyes. At any time, new ASNV, new PDR, new DME and pre-existing DME requiring intervention (see permitted therapies Section 6.5.1), occurring in either eye, classifies a participant as a non-responder. An additional analysis will be conducted for each baseline DRSS level 35 and 43 in the non-study eye to allow for further characterization of RG7774 effects.

In cases where both eyes are eligible, the study eye will be the one with DRSS score of 53. The risk of progression of the disease is higher in eyes with DRSS 53, meaning this population is the one with the higher unmet need (Ip et al. 2015; ETDRS report 1991). If both eyes have the same DR score, then the right eye will be selected as the study eye.

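### The secondary endpoint on vision-threatening events gets counts and percentages only; a risk difference from placebo for each dose, with a 90% CI, would answer its objective better at little cost

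*Combined protocol and SAP*

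**What the plan says.** Table 3 sets the secondary objective "Assess the effect of RG7774 on progression to vision-threatening DR" and gives its endpoint as "Incidence of anterior segment neovascularization (ASNV), new PDR, new DME, and pre-existing DME requiring intervention". Section 2.1 words the same aim as to "further evaluate the potential of RG7774 to prevent progression of DR, as determined by the incidence of sight-threatening events".

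For this endpoint Table 7 (Section 9.4.2) gives one method: "Descriptive summaries of the number, frequency and percentage of participants experiencing the types of events". Section 9.4.2 adds a general rule: "All efficacy data will be summarized by randomized treatment group and visit for the ITT population".

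Neither Table 3 nor Table 7 says whether events count in the study eye or in either eye, or whether they accumulate to Week 36 (end of treatment) or Week 48 (end of the off-treatment period). The other secondary efficacy endpoint, change in BCVA, has both: Week 36, study eye.

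For BCVA, Table 7 names a longitudinal analysis of variance with repeated measures. It is silent on baseline BCVA, the stratification factors, the contrast and the CI level. Section 9.4.2 mentions stratification factors and 90% intervals only in the paragraph on the primary GEE model. Full statistical details are promised in a separate document before any unmasking.

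**The concern.** An objective to assess an effect calls for a comparison with placebo and a statement of its uncertainty. Two columns of percentages leave the reader to form both. Two features of the plan sharpen this.

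- In the same table, a lower-ranked related endpoint (worsening of at least 2 DRSS steps, exploratory) is to be modelled by GEE, while the secondary endpoint gets counts.
- Section 8.3.7 treats development or worsening of DME, ASNV and PDR as natural progression and not as adverse events unless the investigator judges otherwise. The safety tables therefore cannot be relied on to show these events by arm, and this endpoint has to carry them.

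At stake is how informative one of two secondary efficacy results will be in a trial meant to support further development. The eye and window matter even for a descriptive table, because they determine what is counted.

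**Working it through.** **1. The plan's own figures.** Section 9.2 states 74% to 88% power by Fisher's exact test, two-sided 0.10, with 40 completers per arm and 15% versus 40% to 45%. Full enumeration gives 75.5% and 87.5%, which agrees within 2 points. 40/(1 − 0.10) = 44.4, rounded up to 45 per arm and 135 in total, also reproduces. Nothing below changes these figures. They supply n = 40 and 45, and the 90% level matches the two-sided 10% test. No figure is stated for either secondary endpoint.

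**2. Assumed event rate.** Section 4.2.1 cites progression to vision-threatening disease in about 41% within 1 year if untreated. This comes from a cited study and may not transfer. With a constant hazard, also assumed to hold off treatment:

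- Week 36: 1 − (1 − 0.41)^(36/52) = 30.6%
- Week 48: 1 − (1 − 0.41)^(48/52) = 38.6%

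The window alone moves the rate by about 8 points. If counting either eye raised the hazard 1.5 to 2 times (assumption), the Week 36 rate would be 42% to 52%, against 31%.

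**3. Width of the added interval.** Half-width = 1.645 × √[p1(1 − p1)/n + p2(1 − p2)/n], with the drug assumed to halve the placebo rate:

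| Placebo vs drug | n = 45 per arm | n = 40 per arm |
|---|---|---|
| 15% vs 7.5% | 10.9 points | 11.5 points |
| 30.6% vs 15.3% | 14.3 points (CI 1.0 to 29.6) | 15.2 points (CI 0.1 to 30.5) |
| 38% vs 19% | 15.3 points | 16.2 points |

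With no drug effect and 40 per arm, the half-width is 16.9 points at 30.6% and 18.1 points at 41%.

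**4. Why it should be labelled estimation.** Exact Fisher power for 30.6% versus 15.3%, two-sided 0.10, is 43.8% with 45 per arm and 40.5% with 40.

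**5. Denominators by type (invented counts).** Section 4.2.1 caps participants with DME at 50%. If the cap is reached in an arm of 45, about 22.5 are at risk of new DME. Five cases are 5/45 = 11.1% of the arm, but 5/22.5 = 22.2% of those at risk.

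**6. BCVA.** The variance of the baseline-adjusted analysis relative to unadjusted change is k²(1 − ρ²)/(1 + k² − 2ρk), where k is the ratio of the Week 36 SD to the baseline SD and ρ their correlation (all assumed):

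| ρ | 0.5 | 0.7 | 0.8 | 0.9 |
|---|---|---|---|---|
| k = 1 | 0.75 | 0.85 | 0.90 | 0.95 |
| k = 1.25 | 0.893 | 0.981 | 1.000 | 0.950 |

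The reduction is therefore about 0% to 25%.

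**The case against.** The strongest defence is that the descriptive method was chosen deliberately. The protocol calls the study proof-of-concept, exploratory in dose finding and hypothesis-generating. Results will be given by arm, so a reader with counts and denominators can compute a crude difference and interval, and that interval is wide. All of this stands. It lowers the weight of the point but does not remove it: the sponsor can report the difference adjusted for strata, with the right denominators and a fixed eye and window, and a reader of a summary table cannot.

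A second defence is that details are deferred. Section 9.4.2 promises them before unmasking, with missing-data methods also in a separate document. This stands for the BCVA covariates, for how early leavers are counted, and largely for the eye and window.

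Three stronger readings are tempting, and the documents do not support them.

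- *Choices could follow the results.* The commitment to full details before unmasking rules this out as an inference.
- *The eye is settled, or contradicted, elsewhere.* Section 4.2.4 says the same events "occurring in the study eye will classify a participant as a non-responder for the primary analysis", while Section 9.4.2 refers to "Participants in whom any of the events (i) to (iii) described in Section 6.5.3 occur in either eye". Both concern non-response, and their conflict over the primary rule is a separate issue. Section 4.2.4 also has an either-eye rule for the participant-level analysis. The Section 9.4.2 events are linked to rescue and are not identical to the secondary list.
- *Study eye by Week 36 is the intended definition.* This would match the primary and BCVA endpoints. But Table 7 counts participants by event type, Section 4.2.4 expects bilateral effects from an oral drug, and Section 8.1.1 assesses both eyes unless otherwise indicated. Either eye is at least as plausible. Likewise, Section 4.2.4 groups the four events because "as all these events imply progression of the disease", but only to define non-response. That does not make a composite the planned endpoint.

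**Conclusion.** The point holds as a low-cost improvement. The stated method yields no effect estimate with its uncertainty for an objective worded as an effect, and a better method can be applied to data already collected. It is not an error: no stated figure is wrong, no sample size or power figure changes, and a descriptive analysis is defensible here.

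The gain is modest. The half-width of 11 to 16 points assumes placebo rates of 15% to 38% halved on drug, and it reaches about 18 points if rates are high and equal. These figures describe how wide the added interval would be, not a bias in any planned result. The conversion from 41% also assumes a constant hazard and that the cited rate carries over to this population.

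For BCVA the claim is precision only, and the size depends on assumed correlations and SDs. A reader might infer that the plan leaves baseline and strata out of the model. It does not exclude them; it is silent.

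**What to change.** In Table 7 and in the analysis document due before unmasking:

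1. For the event endpoint, add the risk difference for each dose versus placebo with a 90% CI, adjusted for the stratification factors where event counts allow, and label it estimation and not a test.
2. Keep the by-type counts and give each its at-risk denominator, with new DME counted only among those without DME at baseline. Any composite should be additional to the by-type results.
3. State the eye (study eye or either eye) and the cumulative window (Week 36 or Week 48), and show the alternative as supportive. The choice is the sponsor's.
4. For BCVA change, state that the longitudinal model includes baseline BCVA and the three stratification factors, and report the Week 36 difference for each dose versus placebo with a 90% CI.

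The cost is wording and a few extra tables, with no new data, visits or participants. The downside is intervals wide enough to be uninformative if events are few or the effect is small.
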